#### **SYNOPSIS**

# **Study Title**

HypOthermia for Patients requiring Evacuation of Subdural Hematoma: a Multicenter, Randomized Clinical Trial ("The HOPES Trial")

# **Primary Objective**

The objective is to test whether hypothermia improves outcome following TBI with subdural hematoma requiring evacuation. The primary objective is to determine if rapid induction of hypothermia prior to emergent craniotomy for traumatic subdural hematoma (SDH) will improve outcome as measured by Glasgow Outcome Scale-Extended (GOSE) at 6 months.

#### **Secondary Objectives**

**Safety Objective:** To demonstrate the safety of intravascular cooling in the management of acute traumatic SDH.

**Exploratory Objective**: To determine the effect of hypothermia on TBI biomarkers: glial fibrillary acid protein (GFAP) and ubiquitin C-terminal hydrolase (UCH-L1).

**Mechanistic Objective:** To determine if therapeutic hypothermia to 33°C for 48 hours reduces the incidence of cortical spreading depolarization in patients with acute traumatic SDH.

#### **Design and Outcomes**

This is a prospective, pragmatic, randomized, controlled, multi-center trial of the safety and efficacy of intravascular cooling to induce hypothermia in TBI patients prior to and after surgical evacuation of traumatic SDH. **The hypothesis** of the study is that early induction and maintenance of therapeutic hypothermia in patients with TBI undergoing hematoma evacuation will improve global neurologic outcome as measured by GOSE at 6 months. Patients with moderate to severe acute TBI with SDH who require emergent craniotomy will be enrolled into this study. Patients will be randomized into two groups: 1) intervention - rapid induction of hypothermia to 35°C followed by maintenance at 33°C or 2) standard care - normothermia (37°C). All patients will have an intravascular temperature management catheter inserted into the femoral vein.

The trial is aimed for N=120 subjects, but allows an extension up to a maximum of up to 350 patients. The design includes multiple interim looks at the data, after 60, 120, 180, 240, and 300 patients randomized. At each interim, Bayesian predictive probabilities will be used to determine if enrollment should stop before the maximum, either due to futility or expected success.

Patients may have a 6-lead platinum strip electrode placed on the surface of the brain at the time of craniotomy and hematoma evacuation with subsequent monitoring for cortical spreading depression for up to 7 days following injury. The relative incidence of cortical spreading depression in patients treated with hypothermia will be compared against patients treated with normothermia.

Patients will undergo neuropsychological assessment of their level of recovery at 4 weeks and 6 months post-injury. These outcomes assessments will be performed by investigators who are unaware of the treatment group assignment. GOSE (dichotomous: Good recovery and moderate disability will be designated as favorable outcomes; severe disability, vegetative state,

# The HOPES Trial Version 5 02/23/2018

and death as poor outcomes) at 6 months post-injury will be the primary outcome. Disability Rating Scale (DRS) at 4 weeks will be used to impute missing GOS/GOSE scores and will be incorporated into the Bayesian monitoring model.

Patients will have blood and CSF (when available) samples taken at 3 time points [T1, within 6 hrs and as close to time of injury as possible (pre-hypothermia for the treatment arm); T2, post-surgical evacuation of hematoma (7-48 hrs); and T3, 5-14 days post-injury or discharge (DC)], whichever comes first.

# **Study Schematic**

# **Study Schematic** Assess for eligibility +SDH <5hrs post injury Screening Excluded · Not meeting inclusion criteria Declined to participate Other reasons **Enrollment** Randomized (n=350)\* **Allocation** Allocated to normothermia (n= 30-175) Allocated to hypothermia (n= 30-175) Up to 2 L IV fluid Up to 2 L chilled IV fluid Intravascular catheter placed, Intravascular catheter placed, cooled to 35°C **ECoG Monitoring†** prior to opening dura, ECoG Monitoring† Temperature maintained 37°C Maintained at 33°C for 48hrs-5 days Blood/CSF samples T1, T2, T3 Blood/CSF samples T1, T2, T3 Follow-Up 4 week DRS; 6 month DRS, GOSE 4 week DRS; 6 month DRS, GOSE Lost to follow-up Lost to follow-up Discontinued intervention Discontinued intervention **Analysis** Analysed (Intent to treat) Analysed (Intent to treat) □ Excluded from analysis □ Excluded from analysis Analysed as treated Analyzed as treated

†ECoG Monitoring will be performed at approved centers only.

\*Enrollment is intended for N=120 subjects but allows for an extension to a maximum sample size of 350;enrollment may stop after 60, 120, 180, 240, or 300 subjects enrolled, as determined by the results of the interim analyses.

#### **Interventions and Duration**

Patients will be evaluated for enrollment criteria and once confirmed, randomized to standard care (normothermia) or hypothermia. Hypothermia will be initiated immediately after enrollment criteria are confirmed with up to 2 liters of chilled IV fluids. Normothermia patients will receive up to 2 liters of room temperature IV fluids. Intravascular temperature control utilizing the ZOLL CoolGard 3000 or Thermogard XP and femoral catheter ICY or Quattro will be used to induce and maintain normothermia or hypothermia. Normothermia patients will be maintained at 37°C ±0.5°C. Hypothermia patients will be cooled to a temperature of 35°C prior to opening the dura and maintained at a temperature of 33°C±0.5°C. They will remain cooled for at least 48 hours. Cooling may last for up to 5 days in patients who are refractory to re-warming (e.g., intracranial pressure elevates). Re-warming will be controlled at 0.25°C per hour. The intravascular cooling catheter will remain in place for the planned 48 hour cooling and 16-24 hour re-warming periods. However, once the goal temperature (33°C) has been met if for any reason the femoral cooling catheter needs to be removed or if the subject requires extended cooling, a subclavian cooling catheter may be placed or external cooling pads (Arctic Sun) may be used.

#### **Sample Size and Population**

We plan to enroll patients among the clinical sites into two study groups:

- 1. Patients who undergo emergent craniotomy and evacuation of acute subdural hematoma within 6 hours of injury treated with **hypothermia** (intervention).
- 2. Patients who undergo emergent craniotomy and evacuation of acute subdural hematoma within 6 hours of injury treated at **normothermia** (standard care).

Only TBI patients who are not following commands and who require emergent surgical evacuation of an acute subdural hematoma will be enrolled in this study. To reduce the likelihood of imbalance of important prognostic factors between centers, a blocked randomization scheme will be used in this study. Randomization will be divided among the centers by the Biostatistics Center of Berry Consultants.

A randomized design will be used in this study. The trial is intended for N=120 subjects but may extend to a maximum of 350 patients will be randomized equally at a 1:1 ratio to each of two arms (hypothermia versus control). The final analysis will use a one-sided Fisher's exact test with a significance level of 0.02 to compare proportions of patients with good outcome as measured by GOSE at 6 months between two treatment arms. Interim analyses will be performed after 60, 120, 180 240, or 300 patients randomized. The significance level of 0.02 accounts for the multiple interim looks to maintain overall type I error below 0.025. At each interim analysis, we will evaluate the predictive probability of statistical significance with the current sample size and with the maximum sample size. If the predictive probability of statistical significance with 350 patients is sufficiently low, then the study will stop for futility. Otherwise, enrollment will continue to the next analysis. Complete details may be found in Section 9. Operating characteristics of the design, such as power, type I error rate, and average sample size, were assessed by simulation and are described in Section 9.

# HypOthermia for Patients requiring Evacuation of Subdural Hematoma: a Multicenter, Randomized Clinical Trial

#### "The HOPES Trial"

#### 1. STUDY OBJECTIVES

# 1.1 Primary Objective

The primary objective is to determine if rapid induction of hypothermia prior to emergent craniotomy for traumatic subdural hematomas (SDH) will improve outcomes as measured by Glasgow Outcome Scale-Extended (GOSE) at 6 months. Treatment with hypothermia will lead to at least a 15% improvement in good outcomes. The primary outcome measure will be a dichotomized GOSE at 6 months.

#### 1.2 Secondary Objectives

There are four secondary objectives of the study:

**Safety Objective:** To demonstrate the safety of intravascular cooling in the management of acute traumatic SDH.

**Exploratory Objective**: To determine the effect of hypothermia on TBI biomarkers: glial fibrillary acid protein (GFAP) and ubiquitin C-terminal hydrolase (UCH-L1).

**Mechanistic Objective:** To determine if the incidence of cortical spreading depolarization is reduced in patients undergoing therapeutic hypothermia compared to patient undergoing normothermia.

**Impact on Resource Utilization Objective**: To determine the effect of moderate hypothermia on ICU length of stay (LOS) and hospital LOS.

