member whom the clinical site PI has delegated authority to obtain informed consent. The delegation of authority must be documented and a current copy of this document must be maintained at the clinical site. As with all delegated clinical trial responsibilities, it is the responsibility of each site PI to ensure that the delegation is made only to those individuals who are qualified and that there is adherence to all applicable regulatory requirements and Good Clinical Practices (GCP) Guidelines. Additionally, it is the investigator's responsibility to ensure that the patient's legally authorized representative (LAR) has been given an adequate explanation of the purpose, methods, risks, potential benefits and patient responsibilities of the study. In Houston, Cincinnati, Emory and Pittsburgh, if no legally authorized representative is available, Exception from Informed Consent for Emergency Research (EFIC) will be employed. EFIC is not permitted under Florida State law and will not be employed in Miami. EFIC is not permitted at the Japanese sites at this time. The consent form must be an up-to-date document that has been approved by the clinical site's IRB. A sample informed consent form is provided as **Appendix I**.

In this trial, all subjects will have an altered mental status and, therefore, either exception from informed consent will be employed or, when available, informed consent will be obtained from a LAR or person with power of attorney for the patient. Every attempt will be made to contact the patient's LAR/family as soon as possible after the patient's admission, and in accordance with the individual hospital's protocol. To the extent possible, these discussions should be carried out in a private setting without distraction. No coercion will be applied, and the LAR and other family members will be given an opportunity to read the informed consent document, ask and have answered any questions they may have about the study.

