**4.3.4 Randomization Procedure.** Once all eligibility criteria have been confirmed the randomization process will begin. Block randomization within each site will produce a 1:1 ratio between subjects treated with hypothermia and subjects treated with normothermia. Block randomization within each site will be employed for the randomization to enroll comparable numbers of patients among the treatment groups at each trial center. Each study site will have sealed sequentially numbered opaque envelopes with the patient assignment at the respective site. The statistician will generate the study randomization codes using a computer program. The randomization series will yield codes for assignment of subjects to each of the study arms. The codes will be placed in sealed, sequentially numbered opaque envelopes. Envelopes will be opened in sequential order to determine study subject assignment.

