#### 5. STUDY INTERVENTIONS

#### 5.1 Interventions, Administration, and Duration

This is a pragmatic study; patients will be treated with standard care as established at each enrolling center. All of the enrolling sites utilize Brain Trauma Foundation Guidelines as foundation for delivery of care(40). Intravascular cooling catheters may be placed in the emergency room, the operating room or neurotrauma intensive care unit (NTICU). Patients randomized to hypothermia will be rapidly cooled to 35°C before opening the dura and then maintained at 33°C±0.5°C for a minimum of 48 hours and a maximum of 5 days. After evacuation of SDH all patients will be cared for in the ICU by teams experienced in hypothermia and the management of TBI.

Intravascular cooling will be provided by CoolGard 3000 or Thermogard XP which use an intravenous central catheter circulating cooled saline in a closed loop system. These devices

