#### **9.2.2 Secondary outcomes.** Secondary outcomes will include:

- adverse event rates (e.g., infection, pneumonia, hemorrhage, thrombosis)
- ICU LOS, hospital LOS
- incidence of cortical spreading depolarization

• levels of biomarkers (e.g., GFAP, UCH-L1)

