# 9.5 Data Analyses

The primary analysis population will be an Intention-to-Treat population, all randomized subjects, followed by an As-Treated analysis for sensitivity. As described below, for the primary outcome, 4-week DRS will be used to impute missing 6-month GOSE for the interim analyses. Demographic and baseline laboratory results will be summarized using descriptive statistics, including means, standard deviations, medians, ranges, histograms and box-plots. Fisher's exact test and Wilcoxon rank sum test will be used in the data analyses of categorical and continuous variables, respectively. Adverse events will be reported by type, frequency and severity.

9.5.1 Statistical Modeling. The National Acute Brain Injury Study: Hypothermia II (NABIS:H II) shows that there was a strong correlation between 4-week Disability Rating Scale (DRS) and 6month GOSE (Table 1). In particular, there were 2 false negatives out of 45 patients (4%) and 6 false positives out of 30 patients (20%). It shows that the short-term response is a good predictor for 6-month GOSE.

Table 3 summarizes the historical data (NABIS:H II study) comparing the 4-week DRS score and 6-month outcome; 80% (24/30) of good short-term DRS had a good long-term GOSE, while 4% (2/45) poor DRS had a good GOSE:

Table 3

	6-month GOSE		
4-week DRS Score	Poor	Good	Total
Poor (19 or larger)	43 (96%)	2 (4%)	45
Good (18 or less)	6 (20%)	24 (80%)	30

The statistical model used in this study explicitly models the relationship between 4-week DRS and 6-month GOSE score. Let pDc and pDt be the probabilities of good 4-week DRS scores in the control and treatment groups. Furthermore, define

 $p_{Gc0} = Pr(GOSE good | control, DRS poor)$ 

 $p_{Gc1} = Pr(GOSE good | control, DRS good)$ 

pGt0 = Pr(GOSE good | treatment, DRS poor)

pGt1 = Pr(GOSE good | treatment, DRS good)

These probabilities define the conditional probabilities of achieving a good GOSE score given the DRS score and treatment group.

Together, pDc, pDt, pGc0, pGc1, pGt0, and pGt1 define a joint distribution over DRS and GOSE scores. The key parameter of interest is the probability of a good GOSE score within each group, which can be derived from these parameters.

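### The length-of-stay comparison ignores the site blocking used at randomisation, and loses power wherever stay differs between sites

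*Combined protocol and SAP*

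**What the plan says.** ICU and hospital length of stay (LOS) form one of four secondary objectives in Section 1.2 ("To determine the effect of moderate hypothermia on ICU length of stay (LOS) and hospital LOS") and are listed as secondary outcomes in Section 9.2.2 ("ICU LOS, hospital LOS").

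No analysis is written for LOS specifically. The sentence that reaches it is the general one in Section 9.5: "Fisher's exact test and Wilcoxon rank sum test will be used in the data analyses of categorical and continuous variables, respectively". Nothing in Section 9 stratifies or adjusts by site or country. The test is therefore unstratified by omission, not by a stated choice.

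Site is nevertheless a design factor. Section 4.3.4 states: "Block randomization within each site will produce a 1:1 ratio between subjects treated with hypothermia and subjects treated with normothermia". On care, Section 5.1 states that "patients will be treated with standard care as established at each enrolling center", followed by a limiting sentence: "All of the enrolling sites utilize Brain Trauma Foundation Guidelines as foundation for delivery of care". Sections 4.3.3 and 6.3.1 name centres in several US states and refer to sites in Japan ("EFIC is not permitted at the Japanese sites at this time").

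**The concern.** LOS reflects local ICU and discharge practice as well as the patient's course. Nothing in the documents standardises either kind of discharge across centres. Blocking within site balances such differences between the arms, so they largely drop out of the treatment contrast. The plain rank sum test still counts them in its null variance. That variance is then too large for this design, the test rejects less often than its nominal level, and a difference present within every site is harder to detect.

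At stake is how a null LOS result would be read. With the plain test it could mean no effect, or an effect hidden by differences between sites.

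**Working it through.** **What the documents supply.** The plan gives no mean, SD, effect, alpha, sidedness or power for LOS, so there is no LOS figure to reproduce. The one-sided 0.02 level in Section 9.5.1 belongs to GOSE. Taken from the documents: 1:1 blocking within site, 120 patients intended and 350 at most, and possible early stops at 31 and 60.

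**What is assumed.** Two-sided 0.05; normal log-LOS; seven sites with shares 22, 18, 16, 16, 14, 8 and 6%; blocks of 4; ICC (the share of log-LOS variance lying between sites) from 0 to 0.30.

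**Step 1, normal approximation.** With 1:1 blocking within site, the true null variance of the unstratified statistic is about (1 − ICC) times its nominal variance. Hence:
- actual size = 2 × [1 − Φ(1.96/√(1 − ICC))]
- power = Φ(2.80 − 1.96/√(1 − ICC)) where a site-adjusted test has 80%
- sample-size factor = [(1.96/√(1 − ICC) + 0.84)/2.80]²

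At ICC 0.30, 1.96/√0.70 = 2.34. The size is 2 × [1 − Φ(2.34)] = 1.9%, the power Φ(0.46) = 67.7%, and the factor (3.18/2.80)² = 1.29.

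| ICC | Actual size | Power when adjusted test has 80% | Extra patients needed |
|---|---|---|---|
| 0.05 | 4.4% | 78.5% | 4% |
| 0.10 | 3.9% | 76.9% | 8% |
| 0.20 | 2.8% | 72.9% | 17% |
| 0.30 | 1.9% | 67.7% | 29% |

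**Step 2, simulation.** There were 4,000 trials per cell, with simulation error of about 0.3 points on size and 0.7 on power. The effect is 2.80 × √(4/N) within-site SDs, which is 0.51 at N = 120. Three tests were compared: the plain rank sum test, van Elteren by site, and a site-aligned rank test. The aligned test subtracts the site mean, ranks all values together, and takes the permutation variance within site, Σ [n₁n₀/(n(n − 1))] Σ(r − r̄)². Results at N = 120:

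| ICC | Size, plain | Power, plain | Power, van Elteren | Power, aligned | Aligned minus plain |
|---|---|---|---|---|---|
| 0 | 5.1% | 76.8% | 74.7% | 77.0% | 0.3 |
| 0.05 | 4.4% | 76.0% | 75.5% | 77.4% | 1.4 |
| 0.10 | 4.4% | 74.9% | 75.7% | 77.8% | 2.9 |
| 0.20 | 3.2% | 70.8% | 75.1% | 77.2% | 6.5 |
| 0.30 | 2.9% | 66.2% | 75.6% | 77.4% | 11.2 |

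The aligned and van Elteren tests keep a size of 4.5 to 5.6%. A separate simulation, also with seven unequal sites and blocks of 4, gave 61% (plain), 71% (van Elteren) and 73% (aligned) at ICC 0.30, a loss of 12 points with plain-test size 3.0%. At ICC 0.10 it gave a loss of about 1 to 2 points. The simulated size is less extreme than in Step 1, which assumes exact balance in every site and a fixed spread between sites.

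**Step 3, a US/Japan shift only.** Assumptions: N = 120, within-site log-SD 0.7, no other site differences.
- Japanese share 14%, LOS ratio 1.5, 2 or 3: plain power 77, 75 or 70%, against about 78% aligned.
- Japanese share 30%, same ratios: 76, 71 or 60%, against about 77%. Plain-test size falls to 2.1% at ratio 3.

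**Step 4, cost of adjusting in a small trial.** At ICC 0, with the effect rescaled by the same formula:
- N = 31: plain 74.9%, aligned 72.1%, unpooled van Elteren 65.6%.
- N = 60: plain 77.4%, aligned 76.8%, unpooled van Elteren 72.7%.

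Further runs put unpooled van Elteren at 60% against 69% for the plain test at N = 31, and 66% against 72% at N = 60. With ten sites at N = 31 it was 60% against 73%.

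**The case against.** The strongest reply is that nothing here is invalid. The plain test errs on the cautious side, LOS carries no alpha or power claim, and an unadjusted rank test for a secondary outcome is a common choice. The plan also gives grounds to expect modest site differences: all sites work from one guideline ("All of the enrolling sites utilize Brain Trauma Foundation Guidelines as foundation for delivery of care"), and Section 2.1 presents the choice of centres partly as a way to limit variance between them. If the ICC is 0.10 or less, the loss is 3 points at most. The obvious remedy, van Elteren over every site, can do more harm than good in a small trial. Early stopping is a real prospect: Section 9.5.2 allows a futility stop at 31, and Table 6 shows 32 to 34% futility stops at N = 60 under the null.

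Most of this stands. It limits the size of the point and rules out an unpooled van Elteren test. It does not change the direction. A shared guideline and careful choice of centres make a low ICC plausible but do not establish it, and neither covers discharge practice.

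**Conclusion.** The point holds as a conditional, minor loss of efficiency. Wherever LOS differs between sites, the planned test is conservative for a site-blocked design. At N = 120 and two-sided 0.05, the power lost against a site-aligned rank test is about 0 points at ICC 0, 1 to 3 at ICC 0.05 to 0.10, and 6 to 12 at ICC 0.20 to 0.30, where actual size is about 3%. These figures rest on the assumed ICC, number and sizes of sites, block size and alpha. None of these is in the documents.

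A reader might infer more, and the documents do not support it:
- That the LOS p-values are wrong, or that power is certainly lost. Both depend on a between-site variance that the documents do not give; at ICC 0 there is no loss.
- That mixing US and Japanese sites makes the loss large. Neither the number of Japanese sites nor their share of patients is stated.
- That false positives rise or the primary conclusion is affected. Type I error is not inflated, and the GOSE test is a separate analysis.

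**What to change.** In Section 9.5, specify before LOS is analysed that ICU and hospital LOS are compared with a site-aligned rank test using the permutation variance within site, and that a site-adjusted Hodges-Lehmann difference is reported. A van Elteren test is an acceptable alternative only if small sites are pooled by a rule fixed in advance, for example by country.

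The cost is a sentence of text and a few lines of code. If sites do not differ, the aligned test gives up at most about 3 power points should the trial stop near 31 patients, and under 2 points at 60 to 120. An unpooled van Elteren test should not be used: in the runs above it lost about 5 to 6 points at N = 60 and 9 to 13 at N = 31.

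This change does not settle how in-hospital deaths enter LOS. Section 9 has no rule for that, and Section 2.2 cites mortality of 40 to 70% in surgical patients. It is a separate gap.
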